8.2.3.1. Staggered administration of study intervention

The study will be conducted following a staggered design, and the initiation of the HBs-AS37_100 group will be conditional to whether any holding rule is met in the HBs-AS37_50 group.

If ≥ 2 participants from the HBs-AS37 groups are to be vaccinated at the same study site on the same day, these participants should be vaccinated sequentially with at least 60 minutes apart to allow monitoring of any acute event, such as anaphylactic reaction.

During the first SRT review, all available safety data will be reviewed once the first 5 participants in the HBs-AS37_50 group have completed 7 days safety follow-up post-Dose 1 (and data are available for analysis), before administering the second dose to these participants, and before enrolment of the remaining participants in this group in the next cohorts, and the first 5 participants in the HBs-AS37_100 group in the second cohort. The enrolment in the second cohort will start after the second dose is administered to all 20 participants in the first cohort.

During the second SRT review, all available safety data will be reviewed once the first 5 participants in the HBs-AS37_50 group have completed 7 days safety follow-up post-Dose 2, before administering the second dose to the remaining participants in this group in the next cohorts.

During the third SRT review, all available safety data will be reviewed once the first 5 participants of the HBs-AS37_100 group have completed 7 days safety follow-up post-Dose 1, before administering the second dose to these participants, and before enrolment of the remaining participants in this group in the third cohort. The enrolment in the third cohort will start after the third SRT review.

During the fourth SRT review, all available safety data will be reviewed once the first 5 participants in the HBs-AS37_100 group have completed 7 days safety follow-up post-Dose 2, before administering the second dose to the remaining participants in this group, in the third cohort.

Seven days safety follow-up data will also include hematological and biochemical laboratory parameters tested at Day 8 post-study intervention administration.

The investigator can only start vaccinating the participants in the AS37 groups with the second dose or in a subsequent cohort upon notification from the sponsor and receipt of written documentation of a favorable outcome of the scheduled SRT reviews.

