**Table 1      Study interventions**

	Study intervention 1	Study intervention 2	Study intervention 3	Study intervention 4	Study intervention 5
Study intervention name:	Engerix-B	HBsAg/AS03A	Fendrix	HBsAg/AS37B*	HBsAg/AS37A**
Group label	HBs-Alum	HBs-AS03	HBs-AS04	HBs-AS37_50	HBs-AS37_100

\*AS37B refers to aluminum hydroxide + 50 µg CCI [REDACTED]

\*\*AS37A refers to aluminum hydroxide + 100 µg CCI [REDACTED]

- Variable / endpoint:
  - Occurrence of events reported within protocol-defined safety follow-up period.
  - Absolute values post-Dose 1 and 2 and changes from baseline in hematology and biochemistry parameters
- Summary measure:
  - Percentage of participants reporting events within protocol-defined safety follow-up period.
    - For solicited events, the participants not completing the diary are not considered in the denominator (see [Section 6.3.2](#) for details).
    - For unsolicited events, participants not reporting events are considered to be participants without event (see [Section 6.3.2](#) for details).
  - Summary statistics of absolute values post-Dose 1 and 2 and changes from baseline in hematology and biochemistry parameters as well as percentage of participants with abnormal laboratory parameter values, based on the Food and Drug Administration (FDA) grading as presented in Table 22 of the study protocol.

[figure not shown]

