## 3. ANALYSIS SETS

Analysis Set	Description	Analyses Evaluated
Screened	All participants who were screened for eligibility.	Study Population
Enrolled	All participants who entered the study (who were randomized or received study intervention or underwent a post-screening procedure). NOTE: Screening failures (who never passed screening even if rescreened) and participants screened but never enrolled into the study (i.e., met eligibility but not needed) are excluded from the Enrolled Set as they did not enter the study.	Study Population
Exposed (ES)	All participants who received at least 1 dose of the study intervention. Analysis per group using the Enrolled Set is based on the administered intervention.	Safety
Per-Protocol (PPS)	All eligible participants who received all doses as per protocol, had immunogenicity results post-dose, complied with dosing/blood draw intervals, without intercurrent conditions that may interfere with immunogenicity and without prohibited concomitant medication/vaccination.	Immunogenicity

CCI [REDACTED]

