- The number and percentage of participants reporting each individual unsolicited AE category during the 31-day follow up period post-vaccination (i.e., the day of vaccination and 30 subsequent days) will be tabulated with exact 95% CI by event category (e.g., all, grade 3, related, grade 3 related, serious adverse events [SAEs], fatal etc.) for each group, after each dose and overall. Percentages will be computed based on the total number of exposed participants. Participants not reporting an AE will be considered as not having experienced any AE.
- The number and percentage of participants with any unsolicited AEs during the 31-day follow-up period (i.e. the day of vaccination and 30 subsequent days) will be tabulated with exact 95% CI by study group and categorized by Medical Dictionary for Regulatory Activities (MedDRA) system organ class (SOC) and preferred term (PT) (i.e. the table will be grouped by SOC and then preferred terms will be included within each group). Similar tabulation will be done for Grade 3 unsolicited AEs, for any causally related unsolicited AEs, for Grade 3 causally related unsolicited AEs and for unsolicited AEs resulting in a medically attended visit and at least one solicited or unsolicited adverse event excluding SAE. The verbatim reports of unsolicited AEs will be reviewed by a physician and the signs and symptoms will be coded according to the MedDRA Dictionary for Adverse Reaction Terminology. Every verbatim term will be matched with the appropriate preferred term. This will be done by group, after each dose and overall. The summary tables without SOC and PT information will be also produced for the follow-up period lasting until study end.
- The number and percentage of participants reporting each individual unsolicited AE during the 31-day follow-up period (i.e. the day of vaccination and 30 subsequent days) will be tabulated and ranked by MedDRA PT with the most common appearing first. This analysis will be done for each group after each dose and overall.
- The number and percentage of participants with at least one solicited or unsolicited medically attended event (MAE) reported any time between the day of vaccination (Day 1) and the end of the study period post vaccination (up to Day 61 for main analysis, up to Day 361 for final analysis) will be classified by MedDRA SOC and PT and tabulated with exact 95% CI. This analysis will be done by group.

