## 5. SAMPLE SIZE DETERMINATION

A minimum of 23 (and maximum of 30) participants per group will be enrolled in this study. The target sample size has been reduced from 30 to 23 participants per group for reasons of feasibility, as discussed in Section 4.2.1 of the study protocol. [redacted]

[redacted]  
[redacted]  
[redacted]  
[redacted]  
[redacted].

The sample size is not based on formal hypothesis testing and is typical for this kind of study where a treatment is tested for the first-time in human. [redacted]

[redacted]  
[redacted]  
[redacted]  
[redacted]

The primary objectives of the study are to assess the reactogenicity and safety of each vaccine dose throughout the study. [redacted]

[redacted]  
[redacted]  
[redacted].

[figure not shown]
[redacted]  
[redacted]  
[redacted]

[redacted]

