### **6.3.1. Attributing events to vaccine doses**

The dose relative to an event is the most recent study dose given to a participant prior to the start of a given event. For example, if the start date of an AE is between Dose 1 and Dose 2, the relative dose will be Dose 1.

If an event starts on the same day as a study dose, the relative dose will be derived from the additional information provided in the eCRF using the contents of the flag indicating if the event occurred before or after study dose. If 'after study dose' is selected, the relative dose for the event will be the one administered on the start day of the event. If 'before study dose' is selected, the relative dose for the event will be the dose prior to this one.

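### Read literally, the post-Dose 2 unsolicited-AE percentages count participants who never received Dose 2 as event-free, which lowers the rates and their exact confidence intervals

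*SAP*

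**What the plan says.** The first unsolicited-AE bullet of SAP Section 4.2.1 covers the 31-day window and presents percentages with exact 95% CIs "for each group, after each dose and overall". It then fixes the denominator, "Percentages will be computed based on the total number of exposed participants", and the handling of silence: "Participants not reporting an AE will be considered as not having experienced any AE". The primary estimand in SAP Section 1.1 repeats the second rule: "For unsolicited events, participants not reporting events are considered to be participants without event".

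SAP Section 3 defines the Exposed Set as "All participants who received at least 1 dose of the study intervention", so Dose 1 alone is enough. SAP Section 6.3.1 links events to doses: "The dose relative to an event is the most recent study dose given to a participant prior to the start of a given event".

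Elsewhere the SAP uses counts that do vary by dose. Solicited-AE percentages rest on completed symptom screens (Section 4.2.1), eDiary completion rests on dosed participants (Section 6.2.1), and numbers dosed are tabulated by group and dose (Section 6.1.3). None of these is tied to the unsolicited-AE denominator. The later bullets by system organ class and preferred term give no denominator of their own, so the same rule would presumably carry over to them.

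**The concern.** Unsolicited AEs within 31 days after Dose 1 and Dose 2 are a primary endpoint (Protocol Section 3; SAP Section 1.1). Someone who never received Dose 2 has no post-Dose 2 period in which to have an event. Counting that person as event-free pulls the percentage down, towards apparent safety, and by a different amount in each group if Dose 2 uptake differs. The study is meant to differentiate adjuvants, so unequal dilution would also disturb the comparison of groups.

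The protocol provides several routes to a missed Dose 2. Section 7.1.1 lists individual contraindications, after which other study procedures may continue. Sections 7.1 and 7.2 list unwillingness, relocation and loss to follow-up. In the AS37 groups, Section 8.2.3.1 also requires safety reviews; the fourth, for example, takes place "before administering the second dose to the remaining participants in this group, in the third cohort".

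**Working it through.** The plan gives no figure of its own on this point, so there is none to reproduce.

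**Inputs from the documents**
- Group size: "A minimum of 23 (and maximum of 30) participants per group will be enrolled in this study" (SAP Section 5).
- Denominator, definition of exposure and attribution of events: SAP Sections 4.2.1, 3 and 6.3.1.

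**Inputs assumed, because the documents do not give them**
- Participants per group without Dose 2: 0, 1, 2 or 5.
- True post-Dose 2 rate among those given Dose 2: 30%, plus some illustrative event counts.

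**Step 1: who is counted.** Let N be the number exposed in a group, n2 the number given Dose 2, and x the number with an unsolicited AE attributed to Dose 2. By the attribution rule, all x come from the n2. By the denominator rule, all N are counted.

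**Step 2: the formula.** Reported rate = x/N. Rate among those given Dose 2 = x/n2. The first divided by the second is n2/N.

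**Step 3: the size.**

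| N | Without Dose 2 | n2/N | A true 30% is shown as |
|---|---|---|---|
| 23 | 0 | 1.000 | 30.0% |
| 23 | 1 | 22/23 = 0.957 | 28.7% |
| 23 | 2 | 21/23 = 0.913 | 27.4% |
| 23 | 5 | 18/23 = 0.783 | 23.5% |
| 30 | 1 | 29/30 = 0.967 | 29.0% |
| 30 | 2 | 28/30 = 0.933 | 28.0% |
| 30 | 5 | 25/30 = 0.833 | 25.0% |

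For N = 23 the relative understatement is 1 − 22/23 = 4.3% with one missing, 1 − 21/23 = 8.7% with two, and 1 − 18/23 = 21.7% with five. Two groups of 23 with the same true 30% would show 30.0% and 23.5% if one were fully dosed and the other lacked five second doses. That is a gap of 6.5 percentage points produced by the denominator alone.

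**Step 4: the exact (Clopper-Pearson) 95% intervals, N = 23.**
- Two without Dose 2, 8 with an AE: 8/23 = 34.8% (16.4 to 57.3), against 8/21 = 38.1% (18.1 to 61.6).
- Five without Dose 2, 7 with an AE: 7/23 = 30.4% (13.2 to 52.9), against 7/18 = 38.9% (17.3 to 64.3).
- Five without Dose 2, no events: upper limit 14.8% on 23, against 18.5% on 18.

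The intervals move down and also become narrower than the number at risk warrants.

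**Step 5: tables that are not affected.** Everyone in the Exposed Set received Dose 1, so for Dose 1 the two denominators coincide. For the overall column, the full Exposed Set is the appropriate base.

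**The case against.** The best reply is that the sentence was never meant this way. It writes exposed participants in lower case, where the SAP elsewhere uses the abbreviation ES for the defined set. It sits in a bullet about results after each dose, over a window that starts on the day of vaccination. Its evident purpose is to contrast unsolicited events, where non-reporters are kept, with solicited events, where participants without a diary are dropped. Exposed to that dose is therefore a possible reading. It stands as a possibility, but the SAP nowhere states it, the only definition of exposure is at least one dose, and dose-specific counts are worded differently where they are used.

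A second reply is that the estimand population is the Exposed Set, and that restricting to Dose 2 recipients selects people who went on to a second dose. That selection is real and is a reason to label the column clearly. It does not give an undosed participant a post-Dose 2 window, and the overall column keeps everyone.

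Third, the effect may be minor. With one or two missing it is small beside the width of an exact interval at n = 23. All analyses are descriptive, the safety reviews follow a separate SAP, and a careful reader could recover the counts from the exposure table. All of this is correct. It limits the consequence but leaves the stated rule as it is.

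Two stronger inferences are tempting, and the documents do not support them:
- **A group-wide hold.** A reader might picture only the first 5 of 23 HBs-AS37_100 participants receiving Dose 2, which would give a factor of 5/23 = 0.217. This cannot serve as a forecast: the rationale for Protocol Amendment 4 refers to Day 61 post-Dose 2 immunogenicity data from all participants, and Amendment 3 still targeted 23 to 30 in that group.
- **The most reactogenic group is diluted most.** This holds only if that group misses the most second doses. No per-group numbers are given, Dose 2 can be missed in any group for reasons unrelated to safety, and Protocol Section 8.2.3 allows a hold at all sites.

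**Conclusion.** The point holds for the post-Dose 2 unsolicited-AE percentages and their exact CIs, on the literal reading of SAP Sections 3, 4.2.1 and 6.3.1. Relative to the rate among those given Dose 2, the reported rate is too low by the factor n2/N, with more dilution in any group where more participants miss Dose 2, whatever the reason. The size rests on assumed counts: about 4% to 9% relative for 1 or 2 missing in 23, and 23.5% shown for a true 30% with 5 missing. It is zero if all receive Dose 2. It deserves correction because the endpoint is primary and the error runs towards apparent safety. It gives no ground for saying that the trial's results are materially biased.

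**What to change.** Add one sentence to SAP Section 4.2.1, applying to all unsolicited-AE tables by dose:

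> For tables after Dose k, percentages are based on participants in the Exposed Set who received Dose k; for overall tables, on all participants in the Exposed Set.

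Show the number dosed in each column heading. If exposed to that dose was already the intention, the sentence simply records it.

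The cost is one sentence and a table shell change. Section 6.1.3 already produces the counts by group and dose, and no data collection or dosing rule changes. Using the same base for the by-dose concomitant-medication tables (Sections 4.2.1 and 6.1.4) is an optional consistency point: those passages state no denominator, so they contain no error to correct.

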Return of eDiary devices or removal of eDiary application from participant personal device																		○			
Recording of unsolicited events (Days 1-31) post-Dose 1 and post-Dose 2 of study intervention administration		●	●	●	●	●	●	●	●	●	●	●	●	●	●	●	●	●	●	See Section 10.3.8 for more information	
Recording of SAEs, MAEs, pIMDs and pregnancies		●	●	●	●	●	●	●	●	●	●	●	●	●	●	●	●	●	●	See Section 10.3.8 for more information	
Recording of SAEs related to study participation, or to a concurrent GSK medication/vaccine	●	●	●	●	●	●	●	●	●	●	●	●	●	●	●	●	●	●	●	See Section 10.3.8 for more information	
Recording of AEs/SAEs leading to withdrawal from the study		●	●	●	●	●	●	●	●	●	●	●	●	●	●	●	●	●	●	See Section 10.3.8 for more information	
Study Conclusion																				●	See Section 4.5 for more information

V = visit; PC = phone contact; D = day; HBs = Hepatitis B surface antigen; HBc = Hepatitis B core antigen; CMI = cell-mediated immunity; eDiary = electronic diary; SAE = serious adverse event; MAE = medically attended event; pIMD = potential immune-mediated disorder; AE = adverse event; eCRF = electronic case record form; CCI [REDACTED]

CCI [REDACTED].

Note: The double-line border following Day 61 indicates the main analyses that will be performed on all data (i.e., data that are as clean as possible) obtained up to Day 61.

● is used to indicate a study procedure that requires documentation in the individual eCRF.

○ is used to indicate a study procedure that does not require documentation in the individual eCRF.

CONFIDENTIAL

215301 (EARLY-CLINRES-017)
Protocol Amendment 4 Final

1Only for participants in the HBs-alum group.

2Note: Participants with anti-HBs Ab concentration < 100 mIU/mL at Day 361 will be offered a dose of *Engerix-B* after the study.

CCI

[figure not shown]

Table 2 Intervals between study visits

Interval	Optimal length of interval ¹	Allowed interval ²
Screening Visit → Visit 1	7 days	2-28 days
Visit 1 → Visit 2*	1 day	1 day
Visit 2 → PC1	2 days	2 days
PC1 → PC2	2 days	2 days
Visit 1 → Visit 3	7 days	7-8 days
Visit 3 → PC3	2 days	2 days
PC3 → PC4	2 days	2 days
PC4 → PC5	3 days	3 days
Visit 1 → Visit 4	30 days (1 month)	21-42 days
Visit 4 → Visit 5*	1 day	1 day
Visit 5 → PC6	2 days	2 days
PC6 → PC7	2 days	2 days
Visit 4 → Visit 6	7 days	7-8 days
Visit 4 → Visit 7	30 days (1 month)	21-42 days
Visit 4 → Visit 8 ³	150 days (5 months)	136-164 days
Visit 6 → PC8	2 days	2 days
PC8 → PC9	2 days	2 days
PC9 → PC10	3 days	3 days

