3. OBJECTIVES AND ENDPOINTS

Table 3 Study objectives and endpoints

Objectives	Endpoints	Primary
To evaluate the reactogenicity and safety in all study groups.	
 Percentage of participants with solicited administration site and systemic AEs within 14 days (Day 1 till Day 14) after Dose 1 and Dose 2. Duration of solicited AEs (administration site and systemic) after Dose 1 and Dose 2. Percentage of participants with any unsolicited AEs within 31 days (Day 1 till Day 31) after Dose 1 and Dose 2. Percentage of participants with SAEs, MAEs and AEs leading to study withdrawal throughout the entire study period. Percentage of participants with pIMDs throughout the entire study period. The absolute values and changes in hematology and biochemistry parameters post-Dose 1 (Day 8 and Day 31) and post-Dose 2 (Day 38 and Day 61) from baseline (pre-vaccination, Day 1). 	

CONFIDENTIAL

215301 (EARLY-CLINRES-017)

Protocol Amendment 4 Final

Objectives	Endpoints
	
 Percentage of participants with abnormal laboratory parameter values at pre-vaccination (Day 1), post-Dose 1 (Day 8 and Day 31) and post-Dose 2 (Day 38 and Day 61).
	Secondary
To evaluate the humoral immune response in all study groups.	
 GMC of Anti-HBs Ab concentrations at Day 1, Day 31, Day 61 and Day 361. Anti-HBs seroconversion and seroprotection rates at Day 31, Day 61 and Day 361.
	Tertiary
CC1	
To evaluate the cell-mediated immune response induced in all study groups.	
 Frequency of HBsAg-specific CD4+/CD8+ T-cells per 10^6 CD4+/CD8+ T-cells producing at least 2 activation markers including at least 1 cytokine among IFN-γ, IL-2, TNF-α, IL-13, IL-17, 4-1BB and/or CD40L at Day 1, Day 8, Day 31, Day 38, Day 61 and Day 361. Frequency of plasmablasts, T Follicular Helper cells (TFH) and memory B-cells (flow cytometry) at Day 1, Day 8, Day 31, Day 38 and Day 61, in a subset of participants.
CC1	
	
 Frequency of HBsAg-specific memory B-cells (ELISPOT) at Day 1, Day 31, Day 61 and Day 361.
CC1	

AE = adverse event; **SAE** = serious adverse event; **MAE** = medically attended event; **pIMD** = potential immune-mediated disorder; **GMC** = geometric mean concentration; **HBs** = Hepatitis B surface antigen; **Ab** = antibody; **CC1** [REDACTED]

[figure not shown]
CC1 [REDACTED]

CC1 [REDACTED]

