10.3.8.1. Time period for collecting and recording AEs, SAEs, MAEs, pIMDs and pregnancies

All solicited events that occur up to 14 days following administration of Dose 1 and Dose 2 of study intervention (Day 1 to Day 14 and Day 31 to Day 44, respectively) must be recorded into the eDiary, irrespective of intensity. All other AEs occurring within 31 days following Dose 1 and Dose 2 of study intervention administration should be recorded onto the appropriate section of the eCRF, irrespective of their intensity or whether or not they are considered related to the study intervention.

The time period for collecting and recording of SAEs, MAEs, pIMDs, and pregnancies will begin at the first receipt of study interventions and will continue throughout the whole study period.

All AEs/SAEs leading to withdrawal from the study will be collected and recorded from the time of the first receipt of study intervention until the participant is discharged from the study. SAEs related to study participation or to a concurrent GSK medication/vaccine will be collected from the time consent is obtained until the participant is discharged from the study.

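### The study-end summaries of any, Grade 3 and related unsolicited AEs (SAP 4.2.1) would mix complete collection to Day 61 with partial collection for about 300 further days

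*SAP*

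**What the plan says.** **What is tabulated.** SAP 4.2.1 plans tables of unsolicited AEs over a 31-day period after each dose, defined as "i.e., the day of vaccination and 30 subsequent days". The bullet covers any, Grade 3, related and Grade 3 related unsolicited AEs, and those resulting in a medically attended visit. It closes with: "The summary tables without SOC and PT information will be also produced for the follow-up period lasting until study end". The bullet before it sets out a table by event category (all, Grade 3, related, Grade 3 related, SAEs, fatal). That table has exposed participants as the denominator and this rule: "Participants not reporting an AE will be considered as not having experienced any AE".

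**What is collected.** Protocol 10.3.8.1 limits general AE recording: "All other AEs occurring within 31 days following Dose 1 and Dose 2 of study intervention administration should be recorded". The row label in the Schedule of Activities agrees: "Recording of unsolicited events (Days 1-31) post-Dose 1 and post-Dose 2 of study intervention administration". So does the primary endpoint in Protocol section 3: "Percentage of participants with any unsolicited AEs within 31 days (Day 1 till Day 31) after Dose 1 and Dose 2".

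Four kinds of event are collected for longer. On SAEs, MAEs and pIMDs, Protocol 10.3.8.1 says: "The time period for collecting and recording of SAEs, MAEs, pIMDs, and pregnancies will begin at the first receipt of study interventions", continuing for the whole study. On withdrawals it says: "All AEs/SAEs leading to withdrawal from the study will be collected and recorded from the time of the first receipt of study intervention", continuing until discharge from the study.

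**The concern.** The table period and the collection period differ. After the Dose 2 window closes, a mild or moderate unattended AE has no planned route into the database, and neither does a Grade 3 unattended AE that is not serious, not a pIMD and does not lead to withdrawal. A table headed as follow-up to study end would nevertheless present the share of participants with any, Grade 3 or related unsolicited AEs as though the whole year had been observed.

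This is the first study of this antigen with AS37, so a one-year figure for any AE is one that readers will look for. As planned, the figure would be partly a product of the collection schedule, and nothing in the SAP would alert the reader. Protocol 9.3.1 plans unsolicited AEs for the 31-day windows only. The study-end table is therefore an addition, yet SAP 4.8 declares no change to the protocol-defined analyses.

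**Working it through.** **1. Length of the gap.** Inputs are the nominal visit days and Protocol Table 2.

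- Dose 2 is given on Day 31. The window is the dose day plus 30 days, so it closes on Day 31 + 30 = Day 61.
- Study end is Day 361, and 361 − 61 = 300 days. This reproduces the optimal Visit 7 to Visit 9 interval of 300 days in Table 2.
- Covered: 61/361 = 16.9%. Not covered for general unsolicited AEs: 300/361 = 83.1%.

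**2. Range under the allowed visit intervals.** Gap = (Dose 2 to Visit 9) − 30.

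- Four two-dose groups: from 21 + 286 − 30 = 277 to 42 + 314 − 30 = 326 days.
- HBs-alum: from 136 + 166 − 30 = 272 to 164 + 194 − 30 = 328 days.

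**3. Rows affected after Day 61.**

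| Row | Collected to Day 361? | Valid to study end? |
|---|---|---|
| SAE, fatal | Yes | Yes |
| Medically attended | Yes | Yes |
| pIMD | Yes | Yes |
| AE leading to withdrawal | Yes | Yes |
| Any unsolicited AE | Only events that also fall in a row above | No |
| Grade 3, related, Grade 3 related | Only events that also fall in a row above | No |

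**4. Direction of the error.** Take a participant with no recorded event whose only AEs are of the uncollected kind and fall after the Dose 2 window. That participant belongs in the true numerator but is counted as event-free if the no-report rule is carried over. The reported percentage equals the true one minus the share of such participants. The error can only be downward.

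**5. Size in percentage points.** The documents give no AE rate, so this cannot be computed from them. As an illustration only, assume a constant risk p per 31 days of an AE of the uncollected kind. The share with at least one in the collected 61 days is 1 − (1 − p)^(61/31). Over 361 days it is 1 − (1 − p)^(361/31).

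| Assumed p | Seen in 61 days | True over 361 days |
|---|---|---|
| 5% | 9.6% | 45.0% |
| 10% | 18.7% | 70.7% |
| 20% | 35.5% | 92.6% |

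These figures are not a forecast of the planned table. Its any row would also contain attended and serious events to Day 361. Related events are also likely to cluster soon after dosing, which would make their shortfall smaller.

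**6. What removal would lose.** SAP 4.2.1 already plans tables to Day 361 for MAEs, SAEs and pIMDs, and tabulates AEs leading to discontinuation to study end. Among the general rows, the disputed sentence adds only those that the schedule does not support.

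**The case against.** The strongest defence is that the sentence can be read harmlessly. The primary estimand in SAP 1.1 ties its summary measures, including the no-report rule, to the follow-up period that the protocol defines. On that reading each event type is summarised over its own window. The rule counting non-reporters as event-free is written for the 31-day table, so its use at study end is an inference. The table is also supplementary in a purely descriptive study. All of this stands as a limit on the size of the point. It does not remove it: the sentence names study end as the period, does not restrict event type, and the SAP offers no other denominator rule.

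Three stronger readings are tempting, and the documents do not support them.

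- A reader might infer that collection of unsolicited AEs stops altogether at Day 61, so that almost no non-serious events would appear afterwards. Protocol 10.3.4 counts serious events as unsolicited AEs, and non-serious medically attended AEs are collected throughout and would appear.
- A reader might infer that the HBs-alum row would show Dose 3 as free of unattended AEs. The text of Protocol 10.3.8.1 names only Dose 1 and Dose 2, but Protocol Table 11 has Dose 3 columns (D181, D194, D211) whose shading is lost in the available text. If 31 days after Dose 3 were collected, the HBs-alum gap would be 300 − 31 = 269 days and collection would differ between groups. The point is left open.
- A reader might take the illustrative percentages as an estimate of the bias. They rest on assumed constant rates and cover only part of what the row would contain.

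**Conclusion.** The point holds for the any, Grade 3, related and Grade 3 related unsolicited-AE summaries to study end, in the final analysis only. For AEs that are non-serious, unattended, not pIMDs and not leading to withdrawal, about 300 of 361 days (272 to 328 under the allowed visit intervals) lie outside planned collection. The understatement rests on one assumption, that the no-report rule of the 31-day table is carried over. Its direction is then certain, but its size in percentage points is unknown.

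The 31-day primary tables are untouched, and at the Day 61 main analysis the nominal gap is zero. This should be corrected before the final analysis is reported. It does not threaten the primary objective.

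**What to change.** Either of two changes to SAP 4.2.1 is enough:

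- delete the sentence; or
- replace it with: For follow-up until study end, summary tables will be produced only for event types collected throughout the study (SAEs, MAEs, pIMDs and AEs leading to study withdrawal).

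In both cases, keep the any, Grade 3, related and Grade 3 related tables to the 31-day windows. If a wider study-end table is kept, add a footnote that all other unsolicited AEs were collected only for 31 days after Dose 1 and Dose 2. Check Protocol Table 11 first, so that the footnote is right for HBs-alum after Dose 3. A study-end table kept in any form should also be listed in SAP 4.8 as an addition to the protocol-defined analyses.

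The cost is one sentence, or one footnote, and a line in SAP 4.8. No data collection, sample size or primary result changes.
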